3.2 Rationale for Study Design and Control Group

EirGen is developing CTAP101 Capsules for the treatment of SHPT in pediatric patients with stages 3 or 4 CKD and VDI. The active ingredient in CTAP101 Capsules is calcifediol, which is formulated as ER capsules for oral administration.

The present study is designed to compare the efficacy of CTAP101 Capsules to matching placebo with regard to reducing mean plasma iPTH levels by at least 30% from pre-treatment baseline in pediatric patients with stage 3 or 4 CKD and VDI. The study will also examine the safety and tolerability of CTAP101 Capsules compared to placebo. This adequate and well-controlled, randomized and double-blind study provides the best means to evaluate efficacy, safety and tolerability of CTAP101 Capsules because no therapy has yet been approved by the FDA to treat elevated iPTH levels associated with low serum total 25-hydroxyvitamin D levels in pediatric CKD patients. In other studies conducted in adult subjects with stage 3 or 4 CKD and SHPT, administration of placebo therapy for 26-weeks has not been shown to result in untoward effects [Coyne 2006; Coburn 2004]. However, since iPTH values >900 pg/mL have been associated with increased risk of fracture in hemodialysis patients [Jadoul 2006], subjects will be terminated from this study for confirmed iPTH levels >900 pg/mL.

The starting dose of 30 mcg per day is based on the results from two phase 3 studies (CTAP101-CL-3001 and CTAP101-CL-3002) conducted in adults with SHPT, stage 3 or 4 CKD and VDI. Data from these studies demonstrated that steady-state serum 25-hydroxyvitamin D₃ levels were reached after 12 weeks of treatment at daily doses of 30 or 60 mcg of CTAP101 Capsules. Accordingly, upward dose titration is not allowed in the present study until after 12 weeks, when subjects receiving the initial dose of CTAP101 Capsules have attained steady-state blood levels of serum total 25-hydroxyvitamin D. A 26-week treatment period was selected for this study to ensure that steady-state will be attained in subjects who undergo upward dose titration at the beginning of treatment week 13.

Previous PK analyses in adult CKD patients have determined that the $t_{1/2}$ of serum 25-hydroxyvitamin D₃ is approximately 30 days (CTAP101-CL-2008). Consequently, the post-dosing FU period of 6-weeks should be sufficient for determining the $t_{1/2}$ in pediatric patients.

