4 STUDY POPULATION SELECTION

4.1 Study Population

The target population for this study is subjects having ages of 8 to <18 years who have been diagnosed with stage 3 or 4 CKD (as demonstrated by medical history and by an eGFR of ≥ 15 and <60 mL/min/1.73m² at screening) who do not require regular hemodialysis, and present with both VDI (serum total 25-hydroxyvitamin D <30 ng/mL) and SHPT (plasma iPTH >100 pg/mL for stage 3 CKD and >160 pg/mL for stage 4 CKD).

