4.2 Inclusion Criteria

Each subject must meet the following criteria to be enrolled in this study:

1. Cohort 1: Be 12 to <18 years of age and have a body weight of ≥ 40 kg; Cohort 2: be 8 to <12 years of age and have a body weight of ≥ 20 kg.
2. Be diagnosed with stage 3 to 4 CKD at least six months prior to the screening visit, and have an eGFR of ≥ 15 to <60 mL/min/1.73m² at screening.
3. Be without any disease state or physical condition that might impair evaluation of safety or which, in the investigator's opinion, would interfere with study participation, including:
 - a. Serum albumin ≤ 3.0 g/dL;
 - b. Serum transaminase (ALT or SGPT, AST or SGOT) > 2.5 times the upper limit of normal at screening; and,
 - c. Urinary albumin excretion of >3000 mcg/mg creatinine.
4. Exhibit during the initial or, if necessary, a screening visit after washout:
 - a. Plasma iPTH >100 pg/mL (stage 3 CKD) or >160 pg/mL (stage 4 CKD)
 - b. Serum calcium <9.8 mg/dL (corrected for albumin);
 - c. Serum total 25-hydroxyvitamin D <30 ng/mL; and,
 - d. Serum phosphorus >2.5 to ≤ 5.5 mg/dL (12 to <18 years) or ≤ 6.0 mg/dL (ages 8 to <12 years);
5. If taking calcitriol or other 1 α -hydroxylated vitamin D analogs, or cinacalcet, be willing to forgo treatment with these agents for the duration of the study and complete an 8-week washout period prior to commencing treatment in the study.
6. If taking $>1,000$ mg/day of elemental calcium, discontinue or reduce calcium use and/or use non-calcium based therapies for the duration of the study.
7. If receiving $\leq 1,700$ IU/day nutritional vitamin D (ergocalciferol or cholecalciferol) therapy, must agree to remain on a stable dose during the study.
8. If taking $>1,700$ IU/day of nutritional vitamin D, must discontinue or decrease the dose to $\leq 1,700$ IU/day, maintain that dose for the duration of the study, and complete an 8-week washout period prior to commencing treatment in the study provided that serum total 25-hydroxyvitamin D is ≥ 30 ng/mL. The washout period is not necessary if serum total 25-hydroxyvitamin D is <30 ng/mL.
9. If taking any bone modifying treatment that could interfere with study endpoints, must discontinue use of such agent(s) for the duration of the study.

10. Willing and able to comply with study instructions and commit to all clinic visits for the duration of the study.

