6.5 Dispensing Study Drug

As described in [Section 5.6](#) Method of Assigning Subjects to Treatment Groups, the IRS will assign the study drug bottle(s) to the subject at the time of randomization (Visit 3) and at Visit 13. The study coordinator (or designated site personnel) will obtain the study drug assignment from the IRS for each subject and dispense the appropriate drug.

Subjects and their appointed guardians are to be instructed NOT to take study drug if it appears discolored or damaged. Subjects are to be advised that the study drug is to be stored at room temperature, 15-30°C (59-86°F). Protect from light and heat.

Subjects will receive a sufficient number of bottles of study drug at visits 3 and 13. Some bottles will contain CTAP101 Capsules and others may contain a matching placebo, dependent on

individual subject dose assignment. Throughout the treatment period the number of capsules remaining in the bottle will be counted by the investigator or designee and recorded on the drug accountability log at Visits 13 and 22. The bottles will then be returned to the subject. Prior to dispensing new bottle(s) of study drug, the coordinator will collect the previous bottle(s) of study drug. See [Section 5.3 Selection and Timing of Dose for Each Subject](#) for further details of drug dispensation.

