7 STUDY ACTIVITIES

7.1 Screening Period

7.1.1 *Visit 1 (Day -70 to -63)*

- AE Assessment
- A signed ICF will be obtained from the subject prior to any study related procedures
- Review of inclusion/exclusion criteria, including eGFR measurement
- Medical history and demographics: date of birth, gender, race, ethnicity, cause and date of CKD. A complete medical history, including alcohol, tobacco and nicotine-containing product use histories and method of contraception, as appropriate, will be recorded
- Medication History: All prescription and over the counter medication usage for the 28 days prior to visit 1 will be recorded
- General PE (including weight, height and BMI)
- VS measurements
- Urine chemistry
- Blood samples to be drawn prior to dosing and washout (if required):
 - Chemistry (full panel) and hematology
 - Plasma iPTH
 - Serum total 25-hydroxyvitamin D
- Urine pregnancy test (only for females of childbearing potential)
- Washout assessment: Subjects who are taking any vitamin D and/or bone metabolism therapy, including vitamin D supplements ($>1,700$ IU/day of ergocalciferol or cholecalciferol), will discontinue or reduce therapy to ≤ 1700 IU/day for the duration of the study. Subjects taking more than 1000 mg/day of elemental calcium will discontinue or reduce therapy for the duration of the study.
 - If washout is not required proceed to visit 3.
 - If washout is required, proceed to visit 2 after completion of at least 8 weeks of washout.

If the screening values do not meet study entry criteria after visit 1, subject may receive supportive care per the investigator's discretion and be retested once. If values do not fall within study entry criteria on retest, the subject will be considered a screen failure and be withdrawn from the study. Only the screening test(s) that did not meet entry criteria at visit 1 are required to be re-drawn and meet entry criteria at the time of the visit 1 retest.

7.1.2 *Visit 2 (Day -7 to -1)*

This visit is only applicable for subjects requiring washout. Subjects requiring washout will need to undergo visit 2 to confirm study entry laboratory values meet or continue to meet study entrance criteria.

- Review of inclusion/exclusion criteria

- Concomitant medications
- AE assessment
- VS measurements
- Blood samples will be drawn for the following analyses:
 - Chemistry (full panel) and hematology
 - Plasma iPTH
 - Serum total 25-hydroxyvitamin D

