7.1.3 Visit 3 (Day 1)

Subjects will need to confirm study entry laboratory values continue to meet study entrance criteria for serum calcium, phosphorus, total 25-hydroxyvitamin D, and plasma iPTH. This visit should occur after screening values from visit 1 (visit 2 for subjects requiring washout) meet study entry criteria.

- Review of inclusion/exclusion criteria
- Concomitant medications
- AE assessment
- General PE (including weight, height and BMI)
- VS measurements
- 12-lead ECG
- Urine chemistry and urinalysis
- Blood samples will be drawn for the following:
 - Chemistry (partial panel)
 - Plasma iPTH
 - Serum total 25-hydroxyvitamin D
 - Serum 25-hydroxyvitamin D₃, [REDACTED]
 - [REDACTED]
- Urine pregnancy (only for females of childbearing potential)
- Randomization of subject
- Dispense assigned bottles of study drug with dosing instructions

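### A child above the 900 pg/mL iPTH stopping threshold at screening is still eligible and can be randomised, because entry sets only lower iPTH limits

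*Combined protocol and SAP*

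**What the plan says.** **Stopping rule.** Section 3.2 defends 26 weeks of placebo. It then qualifies that defence by citing fracture risk in haemodialysis patients with iPTH above 900 pg/mL, and adds that "subjects will be terminated from this study for confirmed iPTH levels >900 pg/mL". The wording is mandatory. It gives no start date and does not define confirmation.

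**Entry.** Section 4.1 describes the SHPT population as "plasma iPTH >100 pg/mL for stage 3 CKD and >160 pg/mL for stage 4 CKD". Criterion 4a in Section 4.2 repeats these floors. No exclusion criterion in Section 4.3 names iPTH. The other three analytes in criterion 4 (calcium, 25-hydroxyvitamin D and phosphorus) all have upper limits.

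**Route to randomisation.** Section 7.1.1 says "If washout is not required proceed to visit 3". Visit 2 is only for children who need washout. The single Visit 1 retest is for values that fail the entry criteria. At Visit 3 (Section 7.1.3) subjects must "confirm study entry laboratory values continue to meet study entrance criteria for serum calcium, phosphorus, total 25-hydroxyvitamin D, and plasma iPTH". That same visit draws plasma iPTH, randomises the child and includes the step "Dispense assigned bottles of study drug with dosing instructions". Section 6.5 agrees: "Subjects will receive a sufficient number of bottles of study drug at visits 3 and 13".

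**Afterwards.** Section 9.10.1 scores as a non-responder any subject with fewer than two iPTH values in the efficacy assessment period (EAP). Section 6.9 places that period at Visits 19 to 22. Section 5.7 blinds subjects, site staff and sponsor to iPTH.

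**The concern.** The 900 pg/mL rule is the safeguard the protocol offers for keeping children with SHPT on placebo, yet nothing at entry matches it. A value of 950 at Visit 1 passes criterion 4a, triggers no retest, and would pass the Visit 3 re-check if repeated. Following the plan as written can therefore randomise a child, with a 1 in 3 chance of placebo, whom the plan's own safety rule then removes.

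The child undergoes randomisation and a short exposure for no purpose. The trial gains an ITT non-responder whose outcome was largely fixed before dosing, and Section 9.2 plans no replacement. Because iPTH is blinded, the plan gives site staff no clear means of catching the case.

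**Working it through.** **1. The path of a no-washout child at 950 pg/mL**

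| Step | Rule applied | Result |
|---|---|---|
| Visit 1 | Criterion 4a: above 100 (stage 3) or above 160 (stage 4) | 950 passes |
| Retest | Only for values failing entry criteria | Not triggered |
| Visit 2 | Washout children only | Skipped |
| Visit 3 (Day 1) | Same entrance criteria | A second value above 900 also passes |
| Visit 3 (Day 1) | Randomise and dispense | Child is in the ITT population |
| Next value above 900 | Section 3.2 | Termination required |

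**2. When termination falls due**

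Two points are not stated: whether screening values count towards confirmation, and whether the Visit 3 result is awaited before randomisation. For confirmation I borrow the two-consecutive-visits convention of Section 5.4, which was written for dose reduction. Assume every value is above 900.

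| Screening values count? | Visit 3 result awaited? | Outcome |
|---|---|---|
| Yes | Yes | Section 3.2 can remove the child before dosing |
| Yes | No | Randomised; Day 1 sample confirms |
| No | Yes | Passes the floor-only re-check, randomised; Visit 4 (Day 8) confirms |
| No | No | Randomised; Visit 4 (Day 8) confirms |

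The child is randomised in three of the four combinations.

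A washout child first above 900 at Visit 2 is in the same position. One above 900 at both Visit 1 and Visit 2 could be removed before randomisation, but only if Section 3.2 covers screening.

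**3. Why the child becomes a non-responder**

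A second EAP value cannot exist before Visit 20 (Day 155 in Appendix 1). From Day 1 that is 155 − 1 = 154 days; from Day 8 it is 155 − 8 = 147 days. Either way the child leaves long before two EAP values are possible.

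**4. Size**

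Inputs from Section 9.2: 72 active and 36 placebo, response rates 0.4 and 0.1, two-sided Fisher's exact test at 0.05, 20% dropout.

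The plan's own figure reproduces. The continuity-corrected normal formula at 2:1 gives 30 placebo and 90 in total, and 90 × 1.2 = 108. Exact Fisher power at 72/36 with the 20% dropouts scored as non-responders (0.4 × 0.8 = 0.32 against 0.1 × 0.8 = 0.08) is 81.3%, in line with the stated 80%.

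The documents give no baseline iPTH distribution. I **assume** k = 1, 2 or 3 affected children of 108, all removed early.

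- Expected on placebo: k/3.
- Expected active responders lost: k × 2/3 × 0.4.
- Fall in the active response rate: that number divided by 72.
- Power: full enumeration with both response rates multiplied by (1 − k/108).

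| k | On placebo | Active responders lost | Active rate falls by (points) | Power, no other dropout | Power, 20% dropouts as non-responders |
|---|---|---|---|---|---|
| 0 | 0 | 0 | 0 | 92.4% | 81.3% |
| 1 | 0.33 | 0.27 | 0.37 | 92.0% | 80.8% |
| 2 | 0.67 | 0.53 | 0.74 | 91.6% | 80.3% |
| 3 | 1.00 | 0.80 | 1.11 | 91.2% | 79.7% |

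The last column is pessimistic. It adds these removals to a dropout allowance of 0.20 × 108 = 21.6 children, which could absorb them.

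**The case against.** **The rule may remove the child in time.** If screening values count and the Visit 3 result is awaited, two values above 900 are already confirmed and Section 3.2 acts before dosing, whatever the entry re-check says. This stands as an exception. It needs both readings at once, and the plan states neither. Nor may a reader infer that Day 1 always confirms, or that every such child must be terminated: termination needs a second value above 900, and Day 1 is the confirming sample only if screening values count.

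**The safeguard works.** The child is removed within about a week of Day 1, or once the result is reported. A reader might infer 26 weeks on placebo at very high iPTH; the documents do not support that. What remains is a brief exposure and a wasted randomisation.

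**Other routes exist.** Inclusion criterion 3 and exclusion criterion 4 let an investigator keep out a child on medical grounds, and Section 5.3 has an unblinded medical monitor overseeing assignments. Neither criterion names iPTH or requires exclusion, and the monitor is given no iPTH ceiling to apply. How screening iPTH results, or a pass/fail flag, reach sites is not stated, so it would be too strong to say that no site could ever notice.

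**Section 6.8 tolerates high early iPTH.** Its rule for values above 600 pg/mL applies only after 12 weeks, and a 900 ceiling would not align entry with that rule. This is fair, but the 600 rule is permissive and the 900 rule is not. A reader might also see a contradiction between Sections 3.2 and 6.8. There is none: Section 6.8 lists reasons for which an investigator may withdraw a subject, so its silence on 900 is only a drafting gap.

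**The number affected may be zero.** This stands; the 1 to 3 children are assumed.

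**Conclusion.** The point holds in a limited form. The entry criteria and the Visit 3 re-check have no iPTH ceiling to match the mandatory 900 pg/mL rule. A child above 900 at the qualifying screening visit is eligible and, unless Section 3.2 both covers screening and is applied to an awaited Visit 3 result, can be randomised and given study drug. A further value above 900 then requires termination, at Day 1 or about Day 8, and the child counts as an ITT non-responder.

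The conclusion rests on reading confirmation as two consecutive visits. Frequency cannot be derived from the documents and is probably low, since the 900 figure comes from haemodialysis patients. A reader might infer a threat to the primary analysis, but the calculation does not support that: with 1 to 3 children assumed, power falls by at most 1.2 points (92.4% to 91.2%), or 1.6 points (81.3% to 79.7%) on top of the planned dropout. The reason to act is safety and internal consistency, and the correction is inexpensive.

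**What to change.** Add to Section 4.2 or 4.3: a subject with iPTH above 900 pg/mL at the qualifying screening visit (Visit 1, or Visit 2 after washout), confirmed by the permitted screening redraw, may not be randomised. Have the IRS or the central laboratory apply the check, because iPTH is blinded to sites. Once the ceiling is an entrance criterion, Section 6.4.2 already allows a screening redraw for a value outside the entrance range. A child first above 900 on Day 1 or later stays under the termination rule.

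As supporting drafting only, state in Section 6.8 when the 900 rule starts, what counts as confirmed, and who triggers it.

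The cost is one short amendment and one eligibility check. A few children with very high iPTH would become ineligible, and some would need a redraw; the documents do not show how many.

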3.3 Study Duration

Each subject will participate in the study for up to approximately 42-weeks (2-weeks screening/baseline, 8-weeks washout, if required, 26-weeks of treatment with CTAP101 Capsules, and 6-weeks of FU evaluation).

Subjects who participate in Cohort 1 will not be eligible for participation in Cohort 2.

4 STUDY POPULATION SELECTION

4.1 Study Population

The target population for this study is subjects having ages of 8 to <18 years who have been diagnosed with stage 3 or 4 CKD (as demonstrated by medical history and by an eGFR of ≥ 15 and <60 mL/min/1.73m² at screening) who do not require regular hemodialysis, and present with both VDI (serum total 25-hydroxyvitamin D <30 ng/mL) and SHPT (plasma iPTH >100 pg/mL for stage 3 CKD and >160 pg/mL for stage 4 CKD).

4.2 Inclusion Criteria

Each subject must meet the following criteria to be enrolled in this study:

1. Cohort 1: Be 12 to <18 years of age and have a body weight of ≥ 40 kg; Cohort 2: be 8 to <12 years of age and have a body weight of ≥ 20 kg.
2. Be diagnosed with stage 3 to 4 CKD at least six months prior to the screening visit, and have an eGFR of ≥ 15 to <60 mL/min/1.73m² at screening.
3. Be without any disease state or physical condition that might impair evaluation of safety or which, in the investigator's opinion, would interfere with study participation, including:
 - a. Serum albumin ≤ 3.0 g/dL;
 - b. Serum transaminase (ALT or SGPT, AST or SGOT) > 2.5 times the upper limit of normal at screening; and,
 - c. Urinary albumin excretion of >3000 mcg/mg creatinine.
4. Exhibit during the initial or, if necessary, a screening visit after washout:
 - a. Plasma iPTH >100 pg/mL (stage 3 CKD) or >160 pg/mL (stage 4 CKD)
 - b. Serum calcium <9.8 mg/dL (corrected for albumin);
 - c. Serum total 25-hydroxyvitamin D <30 ng/mL; and,
 - d. Serum phosphorus >2.5 to ≤ 5.5 mg/dL (12 to <18 years) or ≤ 6.0 mg/dL (ages 8 to <12 years);
5. If taking calcitriol or other 1 α -hydroxylated vitamin D analogs, or cinacalcet, be willing to forgo treatment with these agents for the duration of the study and complete an 8-week washout period prior to commencing treatment in the study.
6. If taking $>1,000$ mg/day of elemental calcium, discontinue or reduce calcium use and/or use non-calcium based therapies for the duration of the study.
7. If receiving $\leq 1,700$ IU/day nutritional vitamin D (ergocalciferol or cholecalciferol) therapy, must agree to remain on a stable dose during the study.
8. If taking $>1,700$ IU/day of nutritional vitamin D, must discontinue or decrease the dose to $\leq 1,700$ IU/day, maintain that dose for the duration of the study, and complete an 8-week washout period prior to commencing treatment in the study provided that serum total 25-hydroxyvitamin D is ≥ 30 ng/mL. The washout period is not necessary if serum total 25-hydroxyvitamin D is <30 ng/mL.
9. If taking any bone modifying treatment that could interfere with study endpoints, must discontinue use of such agent(s) for the duration of the study.

10. Willing and able to comply with study instructions and commit to all clinic visits for the duration of the study.
11. Female subjects of childbearing potential must be neither pregnant nor lactating and must have a negative urine pregnancy test at the first screening visit.
12. All female subjects of childbearing potential and male subjects with female partners of childbearing potential must agree to use effective contraception (eg, implants, injectables, combined oral contraceptives, intrauterine device, sexual abstinence, vasectomy or vasectomized partner) for the duration of the study.
13. Each subject or their legal representative must be able to read, understand and sign the informed consent form (ICF).

4.3 Exclusion Criteria

Subjects who meet any of the following criteria will be excluded from the study:

1. History of or planned kidney transplant or parathyroidectomy.
2. History (prior three months) of serum calcium ≥ 9.8 mg/dL
3. Use of bisphosphonate therapy or other bone modifying treatment (eg, denosumab) within six months prior to enrollment.
4. Known previous or concomitant serious illness or medical condition, such as malignancy, human immunodeficiency virus, significant gastrointestinal or hepatic disease or cardiovascular event or hepatitis, or physical condition that in the opinion of the investigator may worsen and/or interfere with participation in the study.
5. History of neurological/psychiatric disorder, including psychotic disorder, or any reason which, in the opinion of the investigator makes adherence to a treatment or FU schedule unlikely.
6. Known or suspected hypersensitivity to any of the constituents of either investigational product.
7. Currently participating in, or has participated in, an interventional/investigational study within 30 days prior to study screening.

